(d) Any current clinically significant neurological disorder or medical illness affecting brain function, other than a tic disorder.

(e) Any clinically significant abnormality on preoperative magnetic resonance imaging (MRI).

(f) Any labeled DBS contraindication, and/or inability to undergo presurgical MRI (cardiac pacemaker, pregnancy, metal in body, severe claustrophobia), infection, coagulopathy, inability to undergo an awake operation, significant cardiac or other medical risk factors for surgery.

(g) Current or unstably remitted substance abuse, dependence, or a positive urine toxicology screen.

(h) Pregnancy and women of childbearing age not using effective contraception.

(i) Unable to adhere to operational and administrative study requirements (in the investigators' judgment).

(j) Clinical history of severe personality disorder.

(k) An inability to control suicide attempts, immanent risk of suicide in the investigator's judgment, or a history of serious suicidal behavior. This is defined, using the Columbia-Suicide Severity Rating Scale (CSSRS), as: either *i)* one or more actual suicide attempts in the preceding 3 years the lethality of which is rated at 3 or higher or *ii)* one or more interrupted suicide attempts with a potential lethality judged to result in serious injury or death.

(I) Current diagnosis of body dysmorphic disorder.

[figure not shown]
(m) Evidence of dementia or other significant cognitive impairment on neuropsychological evaluation.

2. Study Design

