(See Overview Figure, below). The study will use a parallel controlled design. Seven to eight patients will be implanted at Butler Hospital/Rhode Island Hospital (a total N of 30), then randomized to receive either 1) double-masked active DBS optimization followed by 3 months of masked active DBS or 2) double-masked sham optimization followed by 3 months of sham DBS. The groups will be matched for baseline YBOCS severity and gender using urn randomization. The primary outcome measure will be improvement in OCD symptoms using the YBOCS as a continuous endpoint. All patients in the sham arm will receive open DBS after three months. We will use secondary measures to determine how DBS affects symptoms which are commonly comorbid in this population (eg, depression or non-OCD anxiety), social and occupational/school functioning, and quality of life, to determine overall benefit at the three month end of masked DBS and after long-term open stimulation. Patients may choose to participate in the following additional studies: FDG PET scans, an O15 PET scan, and/or a study involving learning tasks. All of these studies are intended to illuminate the mechanisms of therapeutic effect of DBS.

To obtain an estimate of practice effects and test-retest reliability coefficients in this patient population for data analysis, we will use the same cognitive battery and testing schedule in a comparison group of OCD patients (N=24, recruited 8 per site,) who would otherwise be candidates for surgery (i.e., meet study entry criteria) but have declined this treatment option.

DBS safety will be assessed with: 1) Adverse effect questionnaires covering multiple domains, including those specific to DBS in this population as observed in our pilot work; 2) A comprehensive neuropsychological battery, including measures of personality features affected by frontobasal systems dysfunction, administered twice, at pre-surgical baseline and after 12 months of open continuation DBS; 3) Neurologic examinations at baseline and after 12 months of open DBS. The study will last for five years in order to obtain long-term effectiveness, safety and tolerability data.

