Raters. Raters and patients will be masked to stimulation status in the controlled study phases and will continue ratings in the open study phases.

Treatment Phase

Device Implantation. Our stereotactic surgical procedure was developed starting in 1999 by the three sites in this application working closely with our Belgian collaborators ([name] et al.). We have refined the targeting empirically, based on stimulation effects, over the past 5 years (Preliminary Studies). Brain lead insertion is under local anesthesia. Neurostimulator (INS) and connecting wire implantation are under general anesthesia. Using coordinates individually determined by stereotactic imaging (MRI and CT), custom tetrapolar brain leads (Medtronic Model 3387 or 3387 IES) are inserted along the trajectory of the anterior limb of each internal capsule (see Nuttin et al., 1999), extending into ventral striatum. An extension wire from the scalp connects each lead to a subcutaneous INS in the chest. After implantation, the patient has an overnight inpatient stay to monitor for possible complications including hemorrhage or infection. The leads and neurostimulators will be implanted either on the same day or two different days as a staged procedure. If the procedure is staged, the first stage will be the implantation of the DBS leads. The second stage will be the connection of the leads to implantable neurostimulator (INS). With either the single or staged procedure, a connector is placed on the distal end of the DBS lead which is placed in a subgaleal pocket. If the surgery is a single stage, the INS will be implanted immediately and connected to the distal end of the lead. If the procedure is staged, then, during the battery placement, a small incision is made over the parietal area to get the distal ends, while leaving the primary incision closed. The extension is tunneled to the incision (e.g., infraclavicular) where the INS is implanted. After implantation of the leads and/or INS, the patient has an overnight inpatient stay to monitor for possible

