The protocol for fear conditioning is identical to that we developed and validated (Milad et al., 2007). Each ER test takes place on two consecutive days at 0, 3, and 6 months. The conditioned stimulus (CS+) is a visual cue, the unconditioned stimulus (UCS) is a mild shock to the fingers, and the measure of conditioned responses is the skin conductance response (SCR). The equipment consists of a “turnkey” differential aversive conditioning system (Coulbourne Instruments, Allentown, PA). In the Conditioning phase, a CS+ (e.g. blue light) is paired with the UCS and a second CS (e.g., red light) is presented during the Conditioning phase and is never paired with the UCS (CS-). The Conditioning phase will consist of a total of 5 CS+ and 5 CS- trials. The shock UCS is delivered immediately following CS+ offset with no delay between the CS+ offset and the UCS onset. After approximately 1 minute, the Extinction Learning phase will begin. During Extinction Learning, 10 CS+ and 10 CS- trials will be presented. On Day 2 (the test day), during the Recall phase, 10 CS+ and 10 CS- trials will be presented. No shocks are delivered during Recall. Contrasting CS+E vs. CS- during extinction recall allows us to assess SCR that are specific for extinction recall.

Subjects will receive \$100 per day (\$200 per two-day session) as compensation for participation. If the subjects withdraw from the study before finishing, they will receive \$20/hr for each hour they participated.

4. Data Analysis

Overall Data Management. The PI and Project Director will be responsible for and supervise data management and data. Data will be stored at in password-protected SPSS version 10 files, on a secure research server with data backup preformed nightly. Hard copies of data capture forms will be kept in locked files to which only authorized study personnel will have access. Descriptive data will be provided for all subject groups (e.g. mean age, sex, education, diagnosis, etc.). Symptom rating scales will be scored as they are in clinical use. Data Analysis will be conducted using SPSS. Data will be analyzed through analysis of variance (ANOVA), followed by appropriate post-hoc analyses.

D. Material Inducements

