“Escape Criteria”: The most likely cause for dropouts will be clinical worsening in the sham condition. If a patient’s symptoms worsen to the point that they become actively suicidal or requires psychiatric hospitalization because of this symptom worsening and a resulting deterioration in functional status, the patient would exit the blinded arm of the protocol and receive open stimulation. Active suicidality will be defined using the Columbia- Suicide Severity Rating Scale (C-SSRS) as an acutal attempt with a lethality rated as 3 or higher, or an interrupted attempt with potential lethality judged to result *in serious injury or death*. Other possibilities include protocol violations or inadvertent breaking of the blind. All potential dropouts will be reviewed by the DSMB for determining whether their data should be included in the analyses.

MRI Scan Risk Management. Here, the most serious risks are from MRI unrelated to the study. Although some MRI procedures can be performed safely in patients who have an implanted DBS system, MRI using a full body radio-frequency (RF) coil or a head transmit coil that extends over the chest area is contraindicated due to the possibility of lead heating and potentially serious brain tissue damage. MRI can also cause induced voltages in the stimulator and/or lead possibly causing uncomfortable, jolting, or shocking levels of stimulation. We inform patient verbally, in the informed consent, and in wallet cards not to have full body MRI, and beyond that ask them to have any physicians contemplating MRI contact us to ensure they do not undergo any contraindicated procedures, including MRI. Often CT scans can be used for diagnosis instead of a body MRI.

Preoperative MRI Risk Management: Participants will be screened using a detailed form to ensure there are no contraindications to undergoing MRI scans (eg, metallic foreign bodies in eyes or head, metal prostheses, severe claustrophobia, pregnancy – screened by a urine pregnancy test). They will be closely monitored to ensure they are as comfortable as possible, and scan time will be kept to the minimum necessary. Patients will be told to alert investigators via intercom if they are distressed so they can be made more comfortable or the scan can be discontinued. Subjects will wear earplugs to reduce the risk of hearing loss from exposure to loud noise during MRI scans.

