board will be chaired by [name], an internationally recognized expert in clinical trials of neuroleptic augmentation for treatment-resistant OCD, and Chair of the Department of Psychiatry at Indiana University. Biostatistics expertise will be provided by [name]., in the Departments of Psychology and Biostatistics at Massachusetts General Hospital. [name] is also a leading expert in behavioral therapies for OCD, including severe cases. [name], a neurologist at the University of Wisconsin, is internationally recognized as expert in the clinical uses and mechanisms of action of DBS for neurologic illness. An additional function of the DSMB will be to review all potential subject dropouts due to protocol violations to determine whether their data should be included in the analyses.

Information on Possible Risks Not Currently Identified. For a previous pilot study, the investigators have an approved Investigational Device Exemption (IDE) reviewing available safety data from Medtronic, Inc. We also monitor our own and collaborators' cumulative experience. Medtronic is also performing ongoing, FDA-mandated studies of the long-term safety and effectiveness the DBS devices in movement disorders. Information that might affect a potential participant's decision to undergo DBS implantation or which might affect a current participants decision to continue DBS may result.

If new significant risks are identified, participants will be informed immediately.

E. Potential Benefits

Although efficacy of DBS for otherwise intractable OCD has not been definitively established (and is not required for approval under the HDE mechanism), the available data indicate that a substantial proportion of patients (half or more) may experience durable clinical benefit from the procedure.

F. Risk-Benefit Ratio

As noted above, intractable OCD is a devastating condition. In our extensive experience over more than 10 years, patients applying for neurosurgical treatment are severely symptomatic. These patients were experiencing profound impairment in social or occupational functioning, in addition to severe subjective distress. They and their treating physicians felt that surgical intervention was the only available option, since they had failed multiple conventional treatments. Suicidal ideation, suicide attempts, and suicide have occurred in this group, including while patients were on waiting lists for surgery.

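### The DSMB decides after randomisation, with no stated criterion, whether a dropout's data are analysed, although dropout is expected mainly from worsening on sham

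*Protocol*

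**What the plan says.** Section III of the protocol, in the Escape Criteria paragraph under protection of the subject, names the expected source of dropout: "The most likely cause for dropouts will be clinical worsening in the sham condition". A patient who meets the escape criteria leaves the masked comparison: "the patient would exit the blinded arm of the protocol and receive open stimulation". The paragraph adds protocol violations and accidental unmasking as other causes, and ends: "All potential dropouts will be reviewed by the DSMB for determining whether their data should be included in the analyses".

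The Data and Safety Monitoring Plan describes the same function more narrowly. There the board is to "review all potential subject dropouts due to protocol violations to determine whether their data should be included in the analyses".

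Three other places bear on the point:

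- Study Design: "The primary outcome measure will be improvement in OCD symptoms using the YBOCS as a continuous endpoint".
- Assignment to Active or Sham Treatment Group: patients are assigned after implantation, 15 per group, before the three masked months. Any ruling on a masked-phase dropout therefore comes after randomisation.
- Data Analysis: "Data will be analyzed through analysis of variance (ANOVA), followed by appropriate post-hoc analyses". This names no analysis set, so it does not override the Escape Criteria paragraph.

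**The concern.** Randomisation makes the two arms comparable only if the patients analysed are those randomised. Here a board rules on individual patients after their course is known, and the protocol gives it no rule to apply. It does not say that the board is masked to arm. Even if it is, the reason for an escape is itself outcome information, because a patient who escapes has got worse.

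The protocol also supplies the mechanism for bias. It expects the patients under review to be mainly sham patients who worsened. Removing them makes the remaining sham group look better than the randomised sham group and shrinks the difference from active stimulation. One patient is 1/15 = 6.7% of an arm. The trial is meant to be definitive, so a diluted estimate, or a result open to challenge over who was counted, is a real cost.

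**Working it through.** **Inputs from the protocol.** 15 patients per arm and a continuous YBOCS endpoint. The protocol gives no alpha, power, SD, effect size or escape rate, so there is no figure of its own to reproduce.

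**Assumptions, for scale only.** Normally distributed improvement with SD 1, a two-sided pooled t-test at 0.05, and a true effect of 1.0 SD. The number of sham escapers k is 1, 2 or 3. The correlation r between the tendency to escape and YBOCS change runs from 0 (unrelated) to 1 (the escapers are exactly the k worst sham patients).

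**Bias.** The three lowest expected values in a normal sample of 15 are -1.736, -1.248 and -0.948, with cumulative sums -1.736, -2.984 and -3.932. Removing the k lowest raises the mean of the remaining sham patients, and so lowers the estimated effect, by r x (absolute cumulative sum)/(15 - k):

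- k = 1: r x 1.736/14 = r x 0.124 SD
- k = 2: r x 2.984/13 = r x 0.230 SD
- k = 3: r x 3.932/12 = r x 0.328 SD

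This shift does not depend on the true effect. At r = 0.5 the estimates are 1 - 0.062 = 0.938, 1 - 0.115 = 0.885 and 1 - 0.164 = 0.836 SD.

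**Power.** By simulation (100,000 trials); with all 30 patients kept, power is 75%.

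| r | Estimate in SD, k = 1, 2, 3 | Power, k = 1, 2, 3 |
|---|---|---|
| 0 | 1.00, 1.00, 1.00 | 74%, 72%, 70% |
| 0.25 | 0.97, 0.94, 0.92 | 71%, 67%, 63% |
| 0.5 | 0.94, 0.89, 0.84 | 69%, 63%, 56% |
| 1 (upper bound) | 0.88, 0.77, 0.67 | 66%, 56%, 45% |

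At r = 0.5 with other assumed effects, power falls from 56% to 49%, 43%, 36% (0.8 SD) and from 89% to 85%, 80%, 75% (1.2 SD).

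**Opposite direction.** Suppose there is no true effect and r = 0.5. Removing one, two or three poorly doing active patients raises the rate of significant findings for DBS from 2.5% to 3.8%, 4.9%, 6.3%. Removing sham patients who did well gives 3.8%, 5.0%, 6.3%. Protocol violations and broken blinds are routes by which either could come before the board.

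**The case against.** **The board is independent and has biostatistical expertise.** That is a safeguard but not a criterion. Careful rulings can still leave groups that differ from those randomised.

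**The board may include everyone.** True. The text permits exclusion and does not require it. A reader might infer that sham escapers will be dropped, but the protocol does not say so. The fault is that the analysed set is open until individual cases have been seen.

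**The intent may be narrower.** The monitoring plan speaks only of protocol violations, and in the Escape Criteria paragraph the board's role directly follows the mention of violations and broken blinds. A reading that leaves escapers out is arguable. The literal wording covers all potential dropouts, however, so the two places need to be reconciled.

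**Escapes will be rare.** Probably so. The escape criteria are narrow, and exclusion criterion (k) keeps out patients with, for example, "one or more actual suicide attempts in the preceding 3 years the lethality of which is rated at 3 or higher". With one escape and r between 0.25 and 0.5, the estimate moves by 0.03 to 0.06 SD and power falls from 75% to 71% or 69%. This limits the likely size of the problem.

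**This belongs in the SAP.** The SAP was not available for this review, and silence on analysis sets would be no finding. Here the protocol itself states a discretionary rule. A reader might infer that a SAP analysing everyone as assigned must contradict it. That goes too far: the protocol speaks of analyses in the plural and names no primary set, so a SAP could apply the board's rulings only to secondary sets.

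**Conclusion.** The concern holds. The protocol gives the DSMB an unguided decision, after randomisation, on whose data are analysed, and in the same paragraph expects the affected patients to be mainly sham patients who worsened. The predicted error is against DBS: on the assumed inputs at r = 0.5, a loss of about 0.06 SD and six percentage points of power for one exclusion, rising to about 0.16 SD and 19 points for three. Effect, SD, correlation and number of escapes are all assumptions.

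Two further inferences are not supported.

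- A reader might conclude that the result could be inflated only by removing poor active-arm patients. Removing sham patients who did well has the same effect, so the discretion can push either way.
- A reader might conclude that keeping escapers with scores taken under open stimulation is worse than excluding them. The protocol says "Raters and patients will be masked to stimulation status in the controlled study phases and will continue ratings in the open study phases", but nowhere that an open-phase score serves as an escaper's masked endpoint. The ranking also depends on the model. At r = 0.5, if the worsening vanishes and the full effect is gained, power is 64%, 52%, 42%, below exclusion. If the worsening persists and the effect is added, it is about 71%, 65%, 59%, slightly above exclusion. At r = 1 with persistent worsening, keeping them is clearly better (72%, 69%, 64% against 66%, 56%, 45%). What stands is that open-stimulation scores dilute the contrast under both models, so their handling must be settled in advance.

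**What to change.** In the Escape Criteria paragraph and the Data and Safety Monitoring Plan:

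1. Replace the case-by-case decision with the rule that the primary analysis includes all randomised patients in their assigned arm.
2. Confine exclusions for protocol violations or broken blinds to a sensitivity set, by criteria fixed in advance and applied masked to arm and outcome.
3. State that YBOCS scores taken under open stimulation after escape are not counted as masked sham response, with their handling fixed before unmasking. The method can sit in the SAP. The last masked rating, baseline or a worst-rank analysis are options, not part of the required change.
4. Give the board's role the same scope in both places.

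The escape criteria and the board's safety role are unchanged. The cost is a few sentences and one sensitivity analysis, with no extra patients or visits. The downside is that any handling of scores after escape rests on an assumption and recovers only part of the lost information.

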board will be chaired by [name], an internationally recognized expert in clinical trials of neuroleptic augmentation for treatment-resistant OCD, and Chair of the Department of Psychiatry at Indiana University. Biostatistics expertise will be provided by [name]., in the Departments of Psychology and Biostatistics at Massachusetts General Hospital. [name] is also a leading expert in behavioral therapies for OCD, including severe cases. [name], a neurologist at the University of Wisconsin, is internationally recognized as expert in the clinical uses and mechanisms of action of DBS for neurologic illness. An additional function of the DSMB will be to review all potential subject dropouts due to protocol violations to determine whether their data should be included in the analyses.

Information on Possible Risks Not Currently Identified. For a previous pilot study, the investigators have an approved Investigational Device Exemption (IDE) reviewing available safety data from Medtronic, Inc. We also monitor our own and collaborators' cumulative experience. Medtronic is also performing ongoing, FDA-mandated studies of the long-term safety and effectiveness the DBS devices in movement disorders. Information that might affect a potential participant's decision to undergo DBS implantation or which might affect a current participants decision to continue DBS may result.

If new significant risks are identified, participants will be informed immediately.

E. Potential Benefits

Although efficacy of DBS for otherwise intractable OCD has not been definitively established (and is not required for approval under the HDE mechanism), the available data indicate that a substantial proportion of patients (half or more) may experience durable clinical benefit from the procedure.

F. Risk-Benefit Ratio

As noted above, intractable OCD is a devastating condition. In our extensive experience over more than 10 years, patients applying for neurosurgical treatment are severely symptomatic. These patients were experiencing profound impairment in social or occupational functioning, in addition to severe subjective distress. They and their treating physicians felt that surgical intervention was the only available option, since they had failed multiple conventional treatments. Suicidal ideation, suicide attempts, and suicide have occurred in this group, including while patients were on waiting lists for surgery.

In summary, patients appropriate for this study are individuals who have been suffering from a prolonged illness that is characterized by immense subjective distress and severe functional impairment, one possible complication of which is death due to suicide (generally undertaken by the patient in an effort to obtain relief from the symptoms of the illness). In this context, the risks of electrode implantation and stimulation, a largely reversible procedure, are justified. The other risks encountered in this study are no different from those of conventional drug and psychotherapeutic treatments of OCD. The risks of a phase of sham stimulation, during which patients may continue to suffer with severe symptoms that have been unresponsive to conventional OCD treatments, will be managed by procedures outlined above, including escape criteria for early activation of the devices if there appears no reasonable clinical alternative. Risks of sham stimulation are inherent in the attempt to acquire controlled data on DBS efficacy in this population.

IV. REFERENCES

Anderson KE, Mullins J (2003): Behavioral changes associated with deep brain stimulation surgery for Parkinson's disease. *Curr Neurol Neurosci Rep* 3:306-13.

Bejjani B, Damier P (1999): Transient Acute Depression Induced by High-Frequency Deep-Brain Stimulation. *NE J Med* 340:1476-80.

Benedict R (1996): Revision of the Brief Visuospatial Memory Test: Studies of normal performance, reliability, and validity. *Psychol Assessment* 8:145-153.

Benedict R (1998): Hopkins Verbal Learning Test - Revised: Normative data and analysis of inter-form and test retest-reliability. *Clin Neuropsychologist* 12:43-55.

Benton AL, Varney NR (1978): Visuospatial judgment. A clinical test. *Arch Neurol* 35:364-7.

